16.3.3 ADCS-ADL

The Alzheimer's Disease Cooperative Study scale for ADL (ADCS-ADL)^{10,11} is administered by an independent rater. The interview was developed to assess impairment of everyday tasks in non-demented individuals with high sensitivity.

16.3.4 CDR

The Washington University Clinical Dementia Rating scale^{12,13} is a structured, clinician-rated interview that collects information on cognitive capacity from both the collateral source and patient for the evaluation of staging severity of dementia. The CDR was developed primarily to assess severity level in persons with dementia but it can be used to stage dementia in other illnesses as well (e.g., Parkinson's disease). Six domains are assessed and then synthesized to assign a Global CDR score. The domains are memory, orientation, judgment and problem solving, community affairs, home and hobbies, and personal care. Impairment is defined only when caused by cognitive loss rather than by physical disability or other non-cognitive factors. Severity ratings range along a 5-point scale (except for the personal care domain):

- CDR-0: no cognitive impairment
- CDR-0.5: questionable or very mild dementia
- CDR-1: mild
- CDR-2: moderate
- CDR-3: severe

The CDR is frequently utilized in clinical and research settings to describe stage-dependent features of dementia and for use as a clinically-meaningful outcome measure in clinical drug trials.

16.3.5 Modified Hachinski Ischemia Score (MHIS)

A modified version of the Ischemic Score of Hachinski uses 4 items of Hachinski's Ischemic Score plus CT findings (if available in subject's history) as a suitable tool for the diagnosis of vascular

dementia.^{14,15} Such a modified ischemic score could comprise 5 items, that is, 4 relevant items of Ischemic Score and the CT features (if available).

1. Abrupt onset (2 points)
2. History of stroke (1 point)
3. Focal neurological symptoms (2 points)
4. Focal neurological signs (2 points)
5. CT-Low density areas isolated (2 points) or multiple (3 points)

Maximum Total Score = 10

A 9-10 point total score points to the existence of old or recent cerebrovascular lesions, simple or multiple.

ICH	International Council for Harmonisation of Technical Requirements for Pharmaceuticals for Human Use
ITT	Intent-to-Treat
LSMeans	Least Square Mean
MMRM	Mixed model for repeated measures
MAR	Missing at Random
MNAR	Missing Not at Random
Max	Maximum
MCI	Mild Cognitive Impairment
MedDRA	Medical Dictionary for Regulatory Activities
MHIS	Modified Hachinski Ischemia Score
Min	Minimum

This document is confidential.

Statistical Analysis Plan**Sponsor:** Tetra Discovery Partners, Inc.; **Protocol No.:** BPN14770-CNS-201

Abbreviation	Description
MMSE	Mini Mental State Examination
N/A	Not Applicable
PP	Per Protocol
PT	Preferred Term
QTc	Corrected QT Interval
RBANS (DMI)	Repeatable Battery for the Assessment of Neurological Status (Delayed Memory Index)
SAE	Serious adverse event
SAP	Statistical Analysis Plan
SD	Standard deviation
SE	Standard Error
SI	Standard International System of Units
SMD	Standardized Mean Difference
SOC	System Organ Class
SOP	Standard operating procedure
TEAE	Treatment-emergent adverse event
TFL	Table, Figure, and Listing
WHO	World Health Organization

This document is confidential.

2. Purpose

The purpose of this statistical analysis plan (SAP) is to ensure that the data listings, summary tables, and figures that will be produced, and the statistical methodologies that will be used, are complete and appropriate to allow valid conclusions regarding the study objectives.

2.1. Responsibilities

Syneos Health will perform the statistical analyses and are responsible for the production and quality control of all tables, figures, and listings.

2.2. Timings of Analyses

The final analysis is planned after all subjects complete the final study visit or terminate early from the main phase of the study and the data processing has been completed to lock the study database. Prior to unblinding the treatment allocations, the per-protocol population will be identified and documented.

Unless otherwise specified, the analysis includes all data collected in the database through the time of the database lock.

Note, there are no planned interim analyses in this study.

This document is confidential.

3. Study Introduction

3.1. Study Objective

In subjects with a clinical diagnosis of early stage Alzheimer's disease (AD) receiving cholinesterase inhibitor therapy:

- To evaluate the efficacy of two dose levels (10 mg bid and 25 mg bid) of BPN14770 as compared to placebo over a 13-week treatment period
- To evaluate the safety and tolerability of BPN14770 10 and 25 mg bid as compared to placebo over a 13-week treatment period
- To obtain pharmacokinetic data on BPN14770 in this subject population.

The outcomes from this study will be used to determine the dose(s) to be used in subsequent Phase 3 studies.

3.2. Brief Description

This is a Phase 2, randomized, double-blind, placebo-controlled, 3-arm, parallel-design study to evaluate the effects of BPN14770 in approximately 255 subjects with a clinical diagnosis of early stage AD. The study will consist of a Screening period of 28 days or less. The Screening period will be followed by a 13-week double-blind treatment period, and a final follow-up visit for safety one week after treatment is concluded.

Randomization will be stratified based on presence or absence of an ApoE4 allele in the subject's genetic profile. Within each stratum, subjects will be randomized in a blinded, balanced fashion to receive either BPN14770 10mg bid, BPN14770 25 mg bid, or matching placebo. A target of 80 evaluable subjects per group (240 total) is planned (see the sample size determination in [Section 3.4](#)). Approximately 85 subjects per group will be enrolled (255 total) in order to account for potential dropouts. Subjects will have a total of eight clinic visits: Screening; Baseline (Day 1); Weeks 1, 2, 4, 8, 13, and the final Follow-up Visit. The screening visit will consist of consenting the subject, obtaining a medical history, full physical exam, height, weight, BMI, ECG, serology and drug testing, chemistry, hematology, urinalysis, ApoE4 testing, pregnancy testing, and cognitive assessments. If the subject fully qualifies for the study, randomization will occur at the Baseline visit following verification of continued eligibility, at which time the subject will receive study medication.

Cognitive testing will occur at each visit, Week 1 through Week 13, but not at the final Follow-up Visit (note, not all cognitive assessments are performed at each visit). Safety assessments will also be performed at each visit, to include adverse event monitoring, vital signs, ECG, and chemistry and hematology. Urinalysis will also be performed at Screening and Baseline and Weeks 1, 4 and 13. Lipid testing will be performed at Baseline and Week 13. Risk of suicidality will be assessed at Screening, Baseline and Weeks 1, 4, and 13.

Pharmacokinetic sampling will be performed at the clinic visits at Weeks 1, 4, 8 and 13.

3.3. Subject Selection

Individuals are eligible for the study if they meet all of the inclusion and none of the exclusion criteria. The inclusion/ exclusion criteria will be assessed during Screening, which will be up to 28 days prior to first

This document is confidential.

study drug administration. Continued subject eligibility will be verified on Baseline at Baseline, prior to randomization. Specifically, subjects must meet the following AD criteria:

- Clinical Dementia Rating (CDR) score of 0.5 or 1 (on a scale from 0 to 3, with higher scores indicating worse outcome), with Memory Box score of 0.5 or greater.
- MMSE score of 20 or greater (range 0 to 30, with lower scores indicating worse outcome)
- RBANS DMI score < 85 (range 40 to 160, with lower scores indicating worse outcome)

See Sections 6.2 and 6.3 in the study protocol for the complete list of all eligibility criteria.

3.4. Determination of Sample Size

The BPN14770-CNS-201 study will enroll 255 subjects (85 per treatment arm), in anticipation of evaluating at least 240 subjects (80 per treatment). The Primary Efficacy Outcome measure will be change from baseline at Week 13 for the Repeatable Battery for the Assessment of Neurological Status - Delayed Memory Index (RBANS DMI).

The normalized mean of the RBANS DMI is 100, with an SD of 15, and the test-retest reliability is 0.80 with no practice effects using alternate versions of the test [Randolph 1998]. RBANS DMI was used in a recent natural history study of Mild Cognitive Impairment (MCI) due to probable AD [Karantzoulis 2013]. In the large amnesic MCI sample (81 subjects), the mean was 73.4 with a SD of 16.5 in a normal distribution. Performance of healthy, age-matched controls was a mean of 101.4 with a SD of 14.4 (81 subjects) yielding estimates of the standard deviation for the DMI from 14.4-16.5. Therefore, the power analysis is based on the assumption that the standard deviation of the response variable is 16.

The power of the proposed study is driven by the assumed difference between BPN14770 25mg (higher dose) and placebo. Based on randomization of 80 subjects per group into the parallel-design study, the probability is 80 percent that the study will detect a treatment difference at a two-sided 0.05 significance level, if the true difference between BPN14770 25 mg and placebo is 7.15 units. Using the standardized mean difference (SMD) to estimate effect size [Faraone 2008], a change of 7.15 units on the DMI score is an effect size of 0.45.

Table 1 provides sample size estimates for 80 percent and 90 percent probability that the study will detect a treatment difference at a two-sided 0.05 significance level assuming the standard deviation of the DMI is 16.

Table 1 Clinical Sample Size (1:1 Active + Placebo) Based on Effect Size (Change From Baseline) And Desired Power

	Number of Subjects Per Group Based on Desired Effect Size (SMD)					
Standardized Mean Difference (SMD)	0.3	0.35	0.4	0.45	0.5	0.75
RBANS DMI change (M1-M2)	4.8	5.6	6.4	7.2	8	12
Number of Subjects (Power 0.8)	176	130	100	79	64	29
Number of Subjects (Power 0.9)	235	173	133	105	86	39

For comparison, a donepezil study reported by Seltzer et al., 2004, randomized a total of 153 subjects (2:1 active vs placebo) and reported treatment benefit at a significance level of 0.03 after 12 weeks of

This document is confidential.

treatment [Seltzer 2004]. In a larger study of mild-to-moderate AD subjects, the effect size of donepezil reported by Rogers et al. 1998 was 0.4 [Rogers 1998], so the assumption of an effect size of 0.45 for BPN14770 in a milder, early AD population, using a sensitive outcome measure, is reasonable.

Therefore, based on clinical trials of donepezil in a similar population, the proposed sample size will provide adequate power to detect a clinically and statistically significant difference of BPN14770 treatment in early AD.

3.5. Treatment Assignment & Blinding

In this randomized, double-blind, placebo controlled, 3-arm, parallel group study, 255 subjects will be assigned to receive one of three treatments via balanced randomization (1:1:1). Randomization will occur separately within each ApoE4 stratum (presence/absence of ApoE4 isoform) to ensure similar numbers of ApoE4 positive subjects are present in each treatment group. The three treatments are:

- A. BPN14770 10mg, twice-daily
- B. BPN14770 25mg, twice-daily
- C. Matched placebo, twice daily

A randomization schedule will be generated by a statistician unassociated with the study execution prior to the start of the study. Subjects will be randomized on Day 1 and receive their bottle of medication that same day.

This is a randomized, double-blind study, meaning that neither site staff nor subject will know what the subject is receiving. Sponsor staff are also blinded to treatment assignments.

Randomization codes will be provided to the Investigator or designee for use in case of an emergency code break requirement. Confirmation of receipt of the randomization code will be required by the Sponsor. The PI or designee will be responsible for maintaining the blind, consistent with protocol design, throughout the study, except in the case of an emergency code break.

The Investigator will be required to notify the Sponsor in the event of any breaking of the blind for any reason. Blinding is not to be broken during the study unless considered necessary by the Investigator for emergency situations for reasons of subject safety. The Investigator should contact the Medical Monitor before breaking the blind. When the blind is broken, the reason must be fully documented.

Except in the event of an emergency code break for an individual subject, the subjects, Investigator, and all other study personnel involved with subject assessments will remain blinded to the actual treatment assignments of the subjects. The Investigator will be ultimately responsible for ensuring that the integrity of the blind is maintained throughout the study.

3.6. Administration of Study Medication

Study drug will be taken by mouth (PO) with water (at least 120 mL = 4 ounces) in the morning and before bed. Subjects should attempt to take study drug at least 30 minutes prior to breakfast and at least one hour after dinner. The first dose should be taken one hour after dinner on Day 1.

This document is confidential.

3.7. Study Procedures and Flowchart

Table 2 shows the schedule of planned study procedures. Every effort should be made to adhere to this procedure schedule.

Table 2 Schedule of Assessments

	Screening	Baseline	Treatment					Follow-Up
	Days -28 thru Day 0	Day 1	Week 1	Week 2	Week 4	Week 8	Week 13 ^e	Week 14
Visit Number	1	2	3	4	5	6	7	8
Target Study Day	---	1	7	14	28	56	91	98
Visit Window			±2	±2	±2	±3	±3	±3
Informed Consent	X							
Eligibility Criteria Confirmed	X	X						
Medical/Surgical History	X	X						
Demographics and Social History	X							
Full Physical Exam	X						X	
Abbreviated Physical Exam		X						X
Height, Weight, BMI	X	X ^a					X ^a	
Vital Signs ^b	X	X	X	X	X	X	X	X
ECGs (single)	X	X	X	X	X	X	X	
Serology (HbsAg, HCV)	X							
Chemistry and Hematology	X	X ^c	X	X	X	X	X ^c	
Lipids		X ^c					X ^c	
ApoE4 testing	X							
Serum Pregnancy ^d	X						X	
Urine Pregnancy ^d		X						
Urinalysis	X	X	X		X		X	
C-SSRS	X	X	X		X		X	
RBANS	X	X	X	X	X	X	X	
MMSE	X	X	X	X	X	X	X	
CGI-I			X	X	X	X	X	
ADCS-ADL		X				X	X	
CDR	X						X	
Hachinski (MHIS-NACC)	X							
PK and Biomarker Sampling		X (biomarkers only)	X		X	X	X	
Randomization		X						
Dispense Medication		X		X	X	X		
First Dose of Medication		X						

This document is confidential.

Statistical Analysis Plan

Sponsor: Tetra Discovery Partners, Inc.; **Protocol No.:** BPN14770-CNS-201

		(PM dose following dinner)						
Daily Medication Administration BID			X-----X					
Medication accountability			X	X	X	X	X	
Prior/Concomitant Medication Recording	X	X	X	X	X	X	X	X
Adverse Event Recording		X	X	X	X	X	X	X
Final Disposition								X

^a Weight only

^b Vital signs include pulse rate, blood pressure, respiration rate, and temperature

^c Fasting for a minimum of 8 hours prior to blood draw is required at Baseline (Day 1) and End of Treatment (Week 13)

^d All females of childbearing potential, even if using birth control)

^e If a subject terminates from the study prior to Week 13, evaluations intended for Week 13 should be completed at discontinuation, if possible.

This document is confidential.

4. Endpoints

4.1. Primary Efficacy Endpoint

The primary efficacy outcome measure is the change from baseline to Week 13 in Repeatable Battery for the Assessment of Neurological Status - Delayed Memory Index (RBANS DMI).

4.2. Secondary Efficacy Endpoints

There are six secondary efficacy outcomes of interest. Change from baseline will be evaluated for each of the outcome measures below:

- RBANS total score
- Alzheimer's Disease Cooperative Study Activities of Daily Living Inventory - Mild Cognitive Impairment version (ADCS-ADL) total score
- Mini-Mental State Evaluation (MMSE) score
- Clinical Dementia Rating sum of boxes (CDR-SB) score
- Modified ADCOMS (m-ADCOMS) Composite Endpoint

The observed values will be assessed for the endpoint below:

- Clinical Global Impression-Improvement (CGI-I) score

4.3. Safety Endpoints

The following safety endpoints will be collected during the study.

- Treatment-emergent adverse events
- Vital signs
- Clinical laboratory evaluations (chemistry, hematology, lipids, urinalysis)
- Electrocardiogram (ECG) measurements

This document is confidential.

5. Analysis Populations

5.1. Screened Population

The Screened Population will include all screened subjects who signed the informed consent form. This population will be used for summaries of subject disposition, and listings unless otherwise specified.

5.3. Safety Population

The Safety Population will include all randomized subjects who received at least one dose of study treatment. Subjects will be analyzed according to treatment received. Specifically, if a subject randomized to placebo takes one (or more) doses of active treatment (e.g., if the subject is dispensed the wrong drug kit at the site), the subject will be analyzed in that active treatment arm for all safety assessments. The Safety Population will be used for all analyses of safety endpoints.

5.4. Modified Intent-to-Treat Population

The modified Intent-to-Treat (mITT) Population will include all randomized subjects who received at least one dose of treatment and returned for at least one follow-up visit with the primary endpoint collected (non-missing). Subjects will be analyzed according to randomized treatment. The mITT Population will be used for all analyses of efficacy endpoints.

5.5. Per Protocol Population

The Per Protocol (PP) Population includes all mITT subjects who received at least one dose of treatment and returned for at least one follow-up visit with no significant protocol violations. Subjects will be analyzed according to randomized treatment. The PP population will be used to evaluate the robustness of the mITT results.

5.6. PK Population

The PK Population will include all subjects in the Safety Population who receive BPN14770, with at least one post-dose blood sample value with a non-missing (valid) plasma concentration of BPN14770.

5.7. Completers Population

The Completers Population (CP) includes all mITT subjects who completed all 13 weeks of treatment with no significant protocol violations. The CP population will be used to evaluate the robustness of the ITT results.

This document is confidential.

5.8. Protocol Deviations

A protocol deviation is any change or alteration from the procedures stated in the study protocol, consent document, recruitment process, or study materials (e.g., questionnaires).

A major protocol deviation is a deviation that has an impact on subject safety, may substantially alter risks to subjects, may have an effect on the integrity of the study data, or may affect the subject's willingness to participate in the study. Major protocol violations may include (but are not limited to): deviation from inclusion/exclusion criteria, withdrawal criteria met during the study but subject was not withdrawn, prohibited concomitant medications, treatment with incorrect study treatment (e.g., in the event a subject is accidentally given the wrong drug kit by the site), and substantial deviations from the dosing schedule.

A minor protocol deviation is a deviation that does not impact subject safety, compromise the integrity of the study data, or affect the subject's willingness to participate in the study.

For this project, the protocol deviation collection will be managed in Clinical Trial Management System (CTMS) by the Site Monitors during the monitoring visits. The project team reviews the protocol deviation categories and classifications, and confirms these with the Sponsor on an ongoing basis. Protocol deviations will be summarized by classifications and categories on the Randomized Population. All protocol deviations will be listed.

Protocol violations that result in exclusion from the PP population will be identified prior to unblinding.

This document is confidential.

6. General Aspects for Statistical Analysis

6.1. General Methods

Unless otherwise specified, continuous endpoints will be descriptively summarized with n, mean, standard deviation (SD), median, minimum (min) and maximum (max). The minimum and maximum will be reported with the same degree of precision (ie, the same number of decimal places) as the raw data. Mean and median will be reported to one degree of precision more than the raw data and standard deviation will be reported to two degrees of precision more than the raw data. In addition, change from baseline values will be calculated at each time point and summarized descriptively. For categorical endpoints, descriptive summaries will include counts and percentages.” See the programmings specifications at the end of this SAP ([Section 14](#)) for more details.

For tabulations, treatments will be sorted, left to right, as Placebo, BPN14770 10 mg, and BPN14770 25 mg. In those cases where a combined column is needed, this will be at the far right as ‘Pooled BPN14770’ (if the 2 active arms) or ‘Total’ (if all 3 treatment arms). All analyses and summary outputs will be generated using SAS® version 9.4 (or higher).

All subject data, including those derived as applicable, will be presented in the subject data listings; listings will display all subjects who were screened and have the related data collected. In general, the subject data listings will be sorted by treatment group, site (if site ID is not part of subject number), subject number and assessment visit and date (and time, if applicable). The summary tables will be presented descriptively by treatment groups and overall, if applicable.

Unscheduled or repeat assessments will not be included in summary tables, but will be included in listings. Unless otherwise specified, if there are multiple results at a given visit/time point, the latest non-missing value within the visit/time point window will be used.

Where statistical models (e.g., mixed models for repeated measures (MMRM), analysis of covariance (ANCOVA)) are used to determine treatment effect estimates, least square means (LSmeans) and the standard error (SE) of the LSMeans will be presented. Plots of changes over time in efficacy endpoints will present these LSMeans (SE) values. Each of these statistical models will include all 3 treatment groups, and thus pairwise comparisons will be made with all treatments contributing to the error estimates.

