11.4. Laboratory Evaluations

Blood samples for chemistry, hematology and lipid testing and urine samples will be collected based on the collection schedule provided in the Schedule of Assessments in [Section 3.7](#) . A list of the clinical laboratory tests that will be performed can be found in Appendix 16.2 of the protocol. A central laboratory will be used to analyze the clinical laboratory samples.

If laboratory values were considered clinically significant by the investigator, the value was to be reported as a TEAE, and thus clinically significant lab values are reported accordingly in the adverse events.

Summary tables will include descriptive statistics for the actual values and changes from baseline by scheduled time point in hematology, chemistry, lipid testing, and quantitative urinalysis test results by treatment group. For qualitative urinalysis parameters, frequency counts and percentages will be presented over time for these categorical data by treatment.

A shift table based on reported lab values classified as low/normal/high will be created for each lab parameter to assess shift from baseline to each subsequent visit. Similarly, a shift table comparing baseline lab value classification to shifts occurring anytime following initial dose by highest classification and lowest clarification will be provided.

All parameters will be converted to consistent units according to the Standard International System of Units (SI) before summarization.

All clinical laboratory results will be listed by site, subject and timing of collection. Out-of-range values will be flagged as low or high where applicable based on lab normal ranges provided by the lab(s). Listings of abnormal hematology and chemistry test results will be provided.

All clinical laboratory parameters will be plotted over time (with mean and SD) by study visit.

This document is confidential.

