11.6. ECG

Single 12-lead ECGs will be performed at clinic visits as specified in [Table 2](#) Schedule of Assessments.

Summary tables by visit and change from baseline to visit for each ECG parameter (Heart Rate, PR interval, QRS interval, QT interval, RR interval, and QTc interval) will be provided.

The overall results of the ECGs recorded as “normal”, “abnormal, not clinically significant (NCS)” or “abnormal, clinically significant (CS)” will be summarized by treatment group at each visit.

12-lead ECG data will be listed by subject and visit.

The ECG analysis will include a careful review of QTcF values. As part of this review, a summary of the number (percent) of subjects with QTcF values (at pre-treatment and then at any time post-first dose) in the following ranges will be provided: ≤ 450 msec, >450 to ≤ 480 msec, >480 to ≤ 500 msec, and >500 msec. This will be performed by visit as well as at ANY time during the double-blind treatment period (where the highest QTcF value will be used for that assessment).

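### The rule in SAP 6.1 that keeps unscheduled and repeat values out of summary tables conflicts with the any-time worst-value tables for QTcF (11.6) and laboratory shifts (11.4)

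*SAP*

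**What the plan says.** Two general rules stand next to each other in SAP 6.1 (General Methods). The exclusion rule is: "Unscheduled or repeat assessments will not be included in summary tables, but will be included in listings". It carries no qualification. The sentence after it deals with several results at one visit, and there "the latest non-missing value within the visit/time point window will be used". That second sentence does yield to anything specified elsewhere in the SAP.

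Two safety tables are described later.

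- SAP 11.6 (ECG) counts subjects in four QTcF ranges: "This will be performed by visit as well as at ANY time during the double-blind treatment period". For the any-time version it adds that this is the one "where the highest QTcF value will be used for that assessment".
- SAP 11.4 (Laboratory Evaluations) has one shift table for each subsequent visit, and also "a shift table comparing baseline lab value classification to shifts occurring anytime following initial dose by highest classification and lowest clarification will be provided".

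Neither 11.4 nor 11.6 mentions unscheduled or repeat values or refers back to 6.1.

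**The concern.** A worst-value table exists to show, for each arm, how many subjects ever reached an extreme. Off-schedule tests are one place where such an extreme may be seen, and the protocol provides for them. Section 8.9 lets the investigator repeat a laboratory test or add others, 8.11 covers additional testing to assess an event, and 9.3.3 has adverse events followed with relevant assessments and laboratory tests. If those results cannot enter the table, a count labelled as any-time is really a count over scheduled visits, and it can only err towards the milder category.

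The programme's history shows why these parameters are watched. Protocol 4.3.1 reports a QTc increase of about 30 msec in female dogs at 100 mg/kg. Section 4.3.2.2 reports ALT and AST increases, each at 20%, in elderly subjects on 40 mg BID. The dog finding was above the 30 mg/kg no-effect level, and 40 mg BID is above both trial doses. Section 4.3.2.2 also reports no clinically significant effect on biochemistry or ECGs in the elderly groups. These findings show why the tables matter, not that harm is expected here.

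**Working it through.** The SAP gives no figure to reproduce on this point. The check sets the rules side by side and then follows one subject through them.

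**Which values are scheduled.** The Schedule of Assessments (protocol 16.1, SAP 3.7) places post-dose ECG, chemistry and hematology at Weeks 1, 2, 4, 8 and 13, which is five occasions. Urinalysis has three (Weeks 1, 4 and 13). Lipids and, under protocol 8.8, glucose have one (Week 13). Early termination has its own planned ECG and laboratory tests (protocol 10.10). SAP 6.4 uses visits as recorded and reassigns only the early termination visit, for efficacy, so windowing does not bring other off-schedule values in.

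**What each rule does to a worst-value table.**

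- The exclusion sentence removes any unscheduled or repeat value. The scheduled value it followed stays. What is lost is an extreme seen only off schedule, or a repeat more extreme than the scheduled value.
- The latest-value sentence, if it applied, would let a later, lower result replace a high one at the same visit.
- The any-time wording in 11.4 and 11.6, if it overrides 6.1, keeps everything.

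**One subject, with assumed values that are not from the documents.** Scheduled QTcF is 440, 445, 485, 448 and 446 msec at Weeks 1, 2, 4, 8 and 13. A repeat at Week 4 gives 452, and one unscheduled on-treatment ECG gives 505.

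| Rule | Values used | Maximum | SAP 11.6 range |
|---|---|---|---|
| Exclusion sentence | 440, 445, 485, 448, 446 | 485 | >480 to ≤500 |
| Latest-value sentence, unscheduled ECG not used | 440, 445, 452, 448, 446 | 452 | >450 to ≤480 |
| All post-dose values | the five scheduled, 452, 505 | 505 | >500 |

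The same subject falls in three different ranges depending on the rule. Under the exclusion sentence the lower repeat (452) does no damage, because 485 remains. The loss comes entirely from the unscheduled 505.

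**How many subjects.** The number misclassified is the number whose extreme occurs only off schedule. Neither document gives a rate of unscheduled or repeat testing, so this cannot be calculated, and zero is possible.

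**The case against.** The strongest reply is that 11.4 and 11.6 already override 6.1. Section 11.6 contrasts by-visit with any-time, capitalises the word ANY and specifies the highest value. Section 11.4 draws the same contrast. A specific rule normally beats a general one. This is a fair reading, and it makes the issue an unresolved conflict rather than a certain loss. It does not settle the matter, because choosing the highest value does not say which records are eligible, and the exclusion sentence allows no exceptions. Two programmers could produce different tables from the same SAP.

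The second reply is that nothing disappears. Section 6.1 keeps these values in listings, and 11.4 adds listings of abnormal hematology and chemistry results. Laboratory values judged clinically significant are reported as TEAEs, protocol 9.1 extends adverse event reporting to other examinations such as ECG, and TEAEs are tabulated by arm. This stands, and a reader who infers that off-schedule findings reach no table at all would be wrong. But the route depends on the investigator's judgement, protocol 9.1 does not require an unverified abnormal laboratory result to be reported, and no listing or TEAE table gives a worst-value count by arm.

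The third reply concerns even-handedness. Testing prompted by adverse events may differ between arms, and more tests mean more chances of an extreme. This also stands. It is a reason for a footnote, and the by-visit tables still compare arms on scheduled assessments.

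Three stronger readings are tempting, and the documents do not support them.

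- A reader might infer that the tables would miss abnormal values in general. Values at scheduled visits are still counted.
- A reader might infer that a high value followed by a lower repeat drops out under either sentence of 6.1. The exclusion sentence leaves the high value in. The latest-value sentence gives way where something else is specified, and 11.4 and 11.6 specify highest or lowest.
- A reader might size the problem from the calendar: the last two gaps between visits are 28 + 35 = 63 of 91 days, and one missed subject is 1/85 = 1.2% of an arm. The first is visit spacing and the second a hypothetical event. Neither measures bias without a rate of unscheduled testing.

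**Conclusion.** The conflict is real and should be resolved, although it is narrow. On a literal reading of 6.1, both any-time tables cover scheduled post-dose visits only and can understate the worst value for a subject whose extreme was seen solely at an unscheduled or repeat test. Any such error runs towards normal. Whether it occurs depends on two things that the documents leave open: whether the programmer treats the any-time wording as overriding 6.1, and whether such off-schedule extremes arise at all. The size is therefore unknown and may be nil. These are descriptive safety tables, and neither the primary analysis nor any test is affected.

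**What to change.** State the following in SAP 6.1 and repeat it in 11.4 and 11.6:

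- Unscheduled and repeat values are excluded from by-visit summaries only.
- The any-time highest and lowest tables (laboratory shifts in 11.4, maximum QTcF in 11.6) use all values after the first dose within each table's stated period, including unscheduled and repeat results.
- The latest-value rule does not apply to those tables.

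No rule for substituting unscheduled values into by-visit tables is needed to resolve this.

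The cost is a few sentences and minor programming. Any-time rates may look slightly less favourable, and subjects tested more often have more chances to show an extreme. A footnote to each table can say so.
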